1.3 Trial Design

This is a phase III, multi-centre, randomised, assessor-blinded, controlled trial of NEL with temporising device (intervention Arm A) vs temporising device alone (standard treatment/Control Arm B) in preterm infants with IVH and PHVD, with internal pilot trial. 100 infants will be recruited over a 3-year period in 12 or more neurosurgical units throughout the United Kingdom.

For a summary of the participant schedule of assessments, please refer to **section 5.2**. The internal pilot study will be conducted over the first 12 months of recruitment, beginning when the first centre opens. This pilot study will have specific aims of assessing recruitment feasibility, barriers to recruitment and protocol adherence. Please refer to **section 8.3.4** for further detail.

1.4 Benefit Risk Assessment

Hydrocephalus secondary to intraventricular haemorrhage is the most important cause of neurological disability after premature birth. The DRIFT studies have demonstrated that early irrigation of blood and its breakdown products leads to an improvement in cognitive scores at two years, which is maintained at ten years (13,19). The DRIFT procedure requires approximately five days of irrigation of the brain through two indwelling catheters on the neonatal intensive care unit. It is difficult to carry out, and is associated with risks of infection, catheter blockage and raised intracranial pressure.

Ventricular endoscopy, in contrast, is a well-established procedure that is carried out routinely by paediatric neurosurgeons. Irrigation of the blood and its breakdown products within the ventricular system is carried out in a controlled procedure, within approximately 30 minutes, under direct vision. It is hypothesized that NEL is equivalent to DRIFT in conferring potential cognitive benefit whilst being a simpler and more deliverable technique.

NEL will be carried out within the same operative procedure as insertion of a clinically indicated temporising device and therefore does not mandate an additional anaesthetic episode. If NEL is successful at demonstrating the cognitive benefits of DRIFT, it will have the added advantage of being reproducible throughout the UK, rather than restricted to one or two dedicated centres in the country. It is not considered to represent a risk to the infant that is higher than standard medical care.

Standard therapy (Arm B- control) involves insertion of a temporising device, which, for a period of time, typically six to eight weeks, allows diversion of CSF from the ventricles. The device can be either a VAD or a VSG. Both are equivalent for this purpose, and different neurosurgical units and the neonatal units with whom they work will have their own preference. They are associated with the same operative and post-operative risk, namely infection, recurring haemorrhage inside the ventricles, new haemorrhage related to ventricular decompression, catheter blockage, failure of absorption of CSF from the subgaleal pocket of a ventricular-subgaleal shunt, seizures, external leakage of CSF, electrolyte disturbance and a very small risk of stroke. In our experience, all these are rare and occur in less than 5% of cases.

The intervention being evaluated in this randomised trial, NEL will be carried out in addition to insertion of a temporising device (Arm A - Intervention). In our experience and in published studies, the additional risks of endoscopic lavage are low, and occur in less than 5% of cases

(21-25). The risks relate to standard neuro-endoscopic surgery and are expected to be lower than the risks of DRIFT. These include infection, further haemorrhage within the ventricles, haemorrhage related to ventricular decompression, seizures, CSF leak, electrolyte disturbance and a <1% risk of brain injury (21-25). These risks are not expected to be significantly higher than insertion of a temporising device alone. In theory the risk of electrolyte disturbance and seizures, related to the presence of lavage fluid within the ventricles, is slightly higher than with insertion of a temporizing device. This will be mitigated by use of warm Ringer lactate solution or artificial CSF, and by monitoring of serum electrolytes post-lavage. These infants are routinely cared for within a neonatal intensive care unit environment and close care and supervision is routine.

Several published studies have suggested that the requirement for permanent CSF diversion through a ventricular peritoneal shunt is reduced after lavage compared to insertion of a temporising device alone (22,24,25). This is a potential additional advantage of NEL that will be evaluated as an exploratory outcome.

The risks associated with NEL will be mitigated by ensuring that patient recruitment will only take place in established paediatric neurosurgical units and will be undertaken by paediatric neurosurgeons who routinely perform a range of neuro-endoscopic procedures. Each paediatric neurosurgical unit is affiliated with a neonatal unit to ensure appropriate neonatal care. A number of meetings have taken place to discuss the technical details of the irrigation procedure, and a surgical consensus statement has been published (28). In addition, a meeting with world experts in endoscopic lavage in this population is planned before commencement of recruitment to enable a wider discussion and sharing of operative nuances, experience and knowledge.

2 Selection of Sites/Investigators

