5.1.2 Secondary Outcomes

The secondary outcome measures are:

- 1. Developmental Measures:
 - a. Motor quotient (MQ): Age equivalent motor score of the Bayley IV divided by corrected age at assessment, measured at 2 years' corrected age
 - b. Language quotient (LQ): Age equivalent language score of the Bayley IV divided by corrected age at assessment, measured at 2 years' corrected age
- 2. Other neurological and functional assessments conducted during the 2-year follow-up visit:
 - a. Presence of seizures during the first 2 years and use of anticonvulsant medication at 2 years.
 - Presence of cerebral palsy (+ accompanying Gross Motor Function Classification System (GMFCS) grade and deficit distribution map using the Classification of SCPE
 - c. Assessment of hearing and vision (British Association of Perinatal Medicine classification)
 - d. Parent report:
 - i. Brief Infant Toddler Social Emotional Assessment (BITSEA)
 - ii. Quantitative Checklist for Autism in Toddlers (Q-CHAT)
- 3. Mortality up to 2 years corrected age.
- 4. NEL & VP shunt related outcomes:

- a. Safety of NEL: Number of Adverse Events, where Adverse Events would include (and not limited to) secondary bleeding in the brain, post-operative infections, temporising device survival, mortality, stroke, seizures, electrolyte disturbances, CSF leak, unexpected readmissions or return to theatre.
- b. Number and type of further surgical procedures, including revision of the temporising drainage device (VAD or VSG), addition of a second temporising device, surgery for loculated or isolated ventricles, and revisions of the VP shunt, if implanted, until two years' corrected age. These infants often need multiple shunt revisions during their first two years of life. We will have a separate CRF to record data related to these unexpected presentations and procedures.
- c. Requirement for permanent VP shunt insertion at 6 months' corrected age. (This is at the discretion of the treating team in the participating centre, according to routine clinical care).
- 5. Quality of life and health economic assessments:
 - a. Health-Related Quality of Life (HRQoL) in children: TNO-AZL Preschool Children's Quality of Life (TAPQOL) to be assessed at 12-months and 2 years' corrected age
 - b. HRQoL in primary caregiver: EuroQoL EQ-5D-5L to be assessed at baseline, 6 months, 12 months- and 2 years' corrected age

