Vision and hearing assessment (BAPM classification) ⁹										х	
Brief Infant Toddler Social Emotional Assessment (BITSEA)										х	
Quantitative Checklist for Autism in Toddlers (Q-CHAT)										х	

¹ Screening and baseline visit can occur on the same day if the infant's parent/guardian(s) have been given time to reflect on the information in the PIS and following a discussion with a medically qualified investigator where they have and been given the opportunity to ask questions.

Standard of care MRI scans may be submitted for review and storage for all infants where available and if performed as standard of care assessment only.

Please see Imaging Transfer Guidelines for further details.

² Review inclusion and exclusion criteria and ensure eligibility prior to enrolment and randomisation.

³ Baseline Visit assessments to confirm eligibility for trial should be performed within 7 days of Surgery (t=0). Baseline EuroQoL EQ-5D-5L Quality of Life questionnaire can be completed within 28 days prior to randomisation as it is not required to confirm eligibility.

⁴ Investigators are required to submit images of Ultrasound scans for review and storage for all infants.

⁵ Haematology – including Haemoglobin, White Blood Cell Count, platelets as per routine standard of care

⁶ Biochemistry – including Sodium, Potassium, as per routine standard of care

- ⁷ Coagulation: including INR or APTT as per routine standard of care
- ⁸ Physical Examination: Including heart rate, temperature, Glasgow Coma Score. Results of routine **Blood tests for Neutrophils Erythrocyte Sedimentation Rate and C-Reactive Protein should be collected if performed as part of routine care.**
- ⁹ Assessments will be performed by a qualified and validated independent clinical development specialist blinded to the treatment arm.
- ¹⁰ CP subtype (SCPE) & Gross Motor Function Classification System (GMFCS) grade will be assessed
- ¹¹ For Arm A (Intervention) patients, details of the NEL procedure will be recorded in addition to Temporising device information
- ¹² Clinical assessment including weight, review of parental concerns
- ¹³ Review of Concomitant medications for prophylactic antibiotics and anti-epileptic medications prescribed.
- ¹⁴ See section 5.2.1 for details about the performing the 2-year clinical follow-up visit

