6.1.1 Adverse Events

Adverse events include:

- an exacerbation (i.e., increase in the frequency or intensity) of a pre-existing illness, episodic event or symptom (initially recorded at the screening/baseline visit), that is detected after trial intervention
- occurrence of a new illness, episodic event or symptom, that is detected after trial intervention

Adverse events do NOT include:

- Medical or surgical procedures: the condition that leads to the procedure is the adverse event
- Pre-existing disease or a condition present before treatment that does not worsen
- Hospitalisation where no untoward or unintended response has occurred

Reporting of Adverse Events

The patient population includes preterm infants who are cared for on a neonatal intensive care for a prolonged period. Due to the nature of the patient population, a high incidence of adverse events can be foreseeable during their hospital stay. Only adverse events deemed as serious (see section 6.1.2) or as notifiable event (see section 6.2) will be recorded for the trial.

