6.2 Notifiable Adverse Events

The following adverse events should be reported within 5 working days using the Notifiable AE CRF:

- 1. New bleed identified on post-operative cranial ultrasound (CTCAE grade 2 and above)
- 2. Unexpected return to theatre for temporising device dysfunction, infection or CSF leak (CTCAE grade 3 and above). CSF infections will be monitored closely and reviewed at Trial Management Group meetings.
- 3. Return to theatre for insertion of an additional temporising device to treat loculated hydrocephalus (CTCAE grade 3 or above) or for a second endoscopic procedure to deloculate the ventricles
- 4. Confirmed or presumed infection associated with the trial procedure (grade 3 and above). This will include superficial (wound) and deep (CNS) infection. Confirmed infection will be where a micro-organism thought to be causative is isolated and presumed is when a micro-organism is not isolated, but the treating clinical team commences antibiotics. Of note, preterm infants may have many sources of infection and the **reporting here is confined to infection associated with the procedure (grade 3 and above).**
- 5. New development of seizures within 48 hours of the intervention (NEL) (grade 3 and above)
- 6. New development of focal neurological deficits within 48 hours of the intervention (NEL) (grade 3 and above)
- 7. Abandoned NEL procedure

Only non-serious AEs which constitute a notifiable event (listed above) should be reported to CCTU (via the trial database) within 5 working days.

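### Secondary outcome 4a counts electrolyte disturbances as adverse events, but sections 6.1.1 and 6.2 keep non-serious ones out of the trial's adverse event data

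*Protocol*

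**What the plan says.** - **Outcome.** Section 5.1.2, outcome 4a, measures the safety of NEL by the number of adverse events. Its open-ended list of examples includes "seizures, electrolyte disturbances, CSF leak, unexpected readmissions or return to theatre".
- **Recording rule.** Section 6.1.1: "Only adverse events deemed as serious (see section 6.1.2) or as notifiable event (see section 6.2) will be recorded for the trial". The reason given is that many adverse events are foreseeable in preterm infants on neonatal intensive care.
- **Notifiable list.** Section 6.2 has seven items: new bleed, unplanned return to theatre, return to theatre for loculation, procedure-related infection, early seizures, early focal deficit and abandoned NEL. None is electrolyte disturbance. The section closes: "Only non-serious AEs which constitute a notifiable event (listed above) should be reported to CCTU". Section 6.4 leaves all other non-serious events in the medical notes.
- **Why this component matters.** Section 1.4: "In theory the risk of electrolyte disturbance and seizures", attributed to lavage fluid left in the ventricles, is put slightly higher than with a temporising device alone. Table 6 lists electrolyte/sodium imbalance as a risk of NEL.
- **Laboratory schedule.** Section 3.6 and Table 1 schedule biochemistry at baseline and at the 24-48 hour visit, without restriction by arm. Table 1, footnote 6, describes it as "including Sodium, Potassium, as per routine standard of care".

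**The concern.** The outcome and the recording rule do not fit together. Outcome 4a says that electrolyte disturbances are counted; sections 6.1.1 and 6.2 stop the non-serious ones from reaching the data from which the count is made. This is one of the two risks that section 1.4 singles out as possibly higher with lavage. The other, seizures, has its own notifiable item. Safety is also part of the trial's stated objective (section 1.2). A low or equal count in the two arms could be reported as reassurance about electrolytes when it partly reflects what was not recorded.

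**Working it through.** The protocol states no figure for this component, so there is none to reproduce. The check has two parts: following an event through the reporting rules, and an illustration of how much might be lost.

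**1. Path of an electrolyte disturbance through the protocol (either arm)**

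| Type of event | Governing text | In the trial's adverse event data? |
|---|---|---|
| Serious | Not on the foreseeable list in 6.1.2.1, so an unforeseeable SAE under 6.1.2.2, reportable within 24 hours whatever the arm or causality | Yes |
| Non-serious | Not among the seven items in 6.2; medical notes only (6.4) | No |
| Abnormal sodium or potassium at baseline or 24-48 hours | Scheduled biochemistry (3.6, Table 1) | As a laboratory value only; no text makes it an adverse event or links it to 4a |

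The seriousness route is restricted for these infants. The note on hospitalisation in section 6.1 confines that criterion to additional or prolonged admission beyond standard care, and they are already inpatients. The important-medical-condition clause could admit some further cases.

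**2. Illustration of the loss**

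Inputs: 50 infants per arm (section 3.3). The true rate p is taken as 5%, the upper bound that section 1.4 gives for complications. The share s of disturbances that are serious is not in the documents; 10%, 25% and 50% are assumed.

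Expected recorded events = 50 × p × s. Chance of no recorded event in the arm = (1 − p × s)^50.

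| s | Expected recorded | Chance of none recorded |
|---|---|---|
| 10% | 50 × 0.05 × 0.10 = 0.25 | 0.995^50 = 78% |
| 25% | 50 × 0.05 × 0.25 = 0.625 | 0.9875^50 = 53% |
| 50% | 50 × 0.05 × 0.50 = 1.25 | 0.975^50 = 28% |
| all recorded | 50 × 0.05 = 2.5 | 0.95^50 = 8% |

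**3. What full recording could show**

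Normal approximation for two proportions, 50 per arm, two-sided 5%: power = Φ[(d − 1.96 × se0) / se1], where d is the difference, se0 the pooled standard error and se1 the unpooled one.

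- Assumed 5% vs 10%, all recorded: se0 = √(0.075 × 0.925 × 2/50) = 0.0527; se1 = √(0.0475/50 + 0.09/50) = 0.0524; power = Φ[(0.05 − 0.1033) / 0.0524] = Φ(−1.02), about 16%.
- Assumed 5% vs 20%: 62% with all recorded, falling to 34%, 19% and 10% if 50%, 25% and 10% of events are serious and only those are recorded.

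The recording rule costs information at any of these values, but full recording would still not give a conclusive test of a slight excess.

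**The case against.** The strongest reply is that the protocol does capture electrolyte problems, by two routes that operate in both arms: serious cases as unforeseeable SAEs, and scheduled sodium and potassium. How laboratory values are graded and tabulated is normally left to the SAP, which section 8.3.1 promises and which is not shown here. Selective recording is also a reasoned choice in this population. Section 1.4 says only that the risk is in theory slightly higher, shortly after stating that NEL risks are not expected to be significantly higher than those of the device alone. Finally, the list in 4a is illustrative, and no separate comparison by arm is specified for each component.

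Much of this stands. A reader might infer that the safety comparison cannot show an electrolyte effect at all, or that the count will be close to zero whatever NEL does. The documents support neither reading. Serious cases are counted, the 24-48 hour values could be compared, and the serious share is not given; at an assumed 50% there is a 72% chance (1 − 0.28) of at least one recorded event in 50 infants at a 5% rate. Nor can one say that values exist for all 100 infants: they are scheduled, as routine care, and the CRF is not shown.

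What does not stand is that the SAP can settle the whole matter. It could derive a laboratory measure from the scheduled samples. It cannot recover non-serious episodes that arise and resolve outside those samples, because the recording rule and the notifiable list are protocol text.

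**Conclusion.** Sections 5.1.2, 6.1.1 and 6.2 conflict for one named component of outcome 4a. As written, the adverse event count captures only serious electrolyte disturbance and understates a risk that section 1.4 and Table 6 associate with NEL. That conclusion follows from the text and needs no assumption. Its size does: the numbers of recorded events depend on an assumed 5% rate and an assumed serious share of 10% to 50%. The defect lies in the outcome definition and the recording rule; section 1.4 contains no error and supplies only the reason why the component matters. It should be corrected, but it does not disable the safety assessment.

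**What to change.** Reconcile section 5.1.2 with sections 6.1.1 and 6.2:

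1. State that the electrolyte component of outcome 4a is derived from the scheduled baseline and 24-48 hour sodium and potassium values, graded identically in both arms against limits set in advance by the trial team, and reported descriptively by arm.
2. Add post-operative electrolyte disturbance to the notifiable events in section 6.2, worded to apply in either arm, so that episodes outside the scheduled sample are recorded. The existing seizure and focal-deficit items are timed from NEL; the new one should be timed from surgery so that it works equally for controls.

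This changes recording and reporting only, not care. The cost is one derived variable, one item on the notifiable-event form and a small amount of extra site reporting. Because power for a small excess is low even with full recording, the result should be presented as descriptive, and the absence of a difference should not be read as evidence of no excess.

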2.1 Site Selection

The trial sponsor has overall responsibility for site and investigator selection and has delegated this role to CCTU.

2.1.1 Study Setting

This trial will take place in 12 or more paediatric neurosurgical units based across the United Kingdom.

A list of participating sites can be obtained upon request from the ENLIVEN-UK Trial Manager at UCL CCTU.

2.1.2 Site/Investigator Eligibility Criteria

Once a site has been assessed as being suitable to participate in the trial, the trial team will provide them with a copy of this protocol.

To participate in the ENLIVEN-UK trial, investigators and trial sites must fulfil a set of criteria that have been agreed by the Sponsor and ENLIVEN-UK Trial Management Group (TMG) and that are defined below.

Eligibility criteria:

- 1. A named clinician is willing and appropriate to take Principal Investigator responsibility
- 2. Suitably trained staff are available to recruit participants, enter data and collect samples.
- 3. Paediatric neurosurgeons in the unit must be experienced in infant neuroendoscopy and NEL and must attend a dedicated trial training session on the NEL procedure arranged by the sponsor.

2.1.2.1 Principal Investigator's (PI) Qualifications and Agreements

The Principal Investigators (PIs) must be willing to sign a PI Declaration (part of the Clinical Trial Site Agreement), to comply with the trial protocol (confirming their specific roles and responsibilities relating to the trial, and that their site is willing and able to comply with the requirements of the trial). This includes confirmation of appropriate qualifications (provide an up-to-date CV), familiarity with procedure and agreement to comply with the principles of GCP. The PI must agree to permit monitoring and audit as necessary at the site, and to maintain documented evidence of staff who have been delegated significant trial related duties.

2.1.2.2 Resourcing at site

- The investigator should demonstrate potential for recruiting the required number of suitable participants within the agreed recruitment period.
- The investigator should have sufficient time to properly conduct and complete the trial within the agreed trial period.
- The investigator should have available an adequate number of qualified staff and suitable facilities for the anticipated duration of the trial in order to conduct the trial properly and safely.
- The investigator should ensure that all persons assisting with the trial are adequately informed about the protocol, intervention, and their trial-related duties and functions.
- The site should have sufficient data management resources to allow prompt data return to the CCTU (refer to the Data Management Plan for timelines).

2.2 Site approval and activation

Site training will be performed prior to the activation of each site and will include all processes for the trial including but not limited to protocol training, data management procedures, procedures for the intervention, adverse event reporting procedures, procedures for laboratory samples and frequency and expectations for monitoring visits. A log of Site Initiation Visit attendees will be kept in the Trial Master File (TMF) as a record of participants present. The Visit may occur in person or via Videoconference as outlined in the Quality Management and Monitoring Plan (QMMP).

The Trial Manager or delegate will notify the PI in writing of the plans for site activation. Sites will not be permitted to recruit any patients until a letter for activation has been issued. On receipt of the signed Clinical Trial Site Agreement (including the signed PI Declaration), completed delegation of responsibilities log and staff contact details, the Trial Manager or delegate will complete the green light process and issue written confirmation of site activation to the site PI.

The site must conduct the trial in compliance with the protocol as agreed by the Sponsor and, by the Ethics Committee (EC). The PI or delegate must document and explain any deviation from the approved protocol and communicate this to the trial team at CCTU.

A list of activated sites may be obtained from the Trial Manager.

3 Selection of Participants

There will be **NO EXCEPTIONS** (waivers) to eligibility requirements at the time of trial entry. Questions about eligibility criteria should be addressed PRIOR to attempting to randomise a participant.

The eligibility criteria for this trial have been carefully considered and are the standards used to ensure that only medically appropriate participants are entered. Participants not meeting the criteria should not be entered into the trial for their safety and to ensure that the trial results can be appropriately used to make future treatment decisions for other people with similar

diseases or conditions. It is therefore vital that exceptions are not made to these eligibility criteria.

Participants will be considered eligible for enrolment in this trial if they fulfil all the inclusion criteria and none of the exclusion criteria as defined below.

